6 HYPOTHESES TO BE TESTED

There are no formal hypotheses being tested, as the study is primarily a safety and PK evaluation study.

7 SAMPLE SIZE CONSIDERATIONS

The cohort size of 6 subjects receiving the active drug is generally accepted for first-in-humans clinical trials that provide a reasonable sample size for PK parameter estimates (Shen et al). Administration of kindolor tosylate to 6 subjects in each dose group provides a 47%, 62%, 74%, or 82% probability of observing at least 1 occurrence of any AE with a true incidence rate for a given dose group of 10%, 15%, 20%, or 25%, respectively. Furthermore, it will be assumed that pooling the data for the subjects who received placebo (2 from each cohort) provides an adequately sized control group.

8 PROCEDURE FOR UNBLINDING DATA

This study is a double-blind study. If the treatment assignment for an individual subject needs to be unblinded during the trial, the PI will contact the unblinded sponsor or data management center staff for the treatment assignment. A note to the file will be prepared by the person who performed the unblinding to indicate when the subject was unblinded, why the subject was unblinded, and to whom the unblinding information was given.

Blinding and unblinding procedures will be performed in accordance with Fast-Track's SOPs CT017 Procedures for Unblinding Investigational Agent Identity for a Study or a Single Subject, CT024 Preparation of Randomization Codes and Maintenance of Treatment Assignment Schedules, CT033 Security and Access to Clinical Trial Databases, and CT045 Development of Clinical Data Management Plans.

At the completion of the study, after the database has undergone edit checking and QA audit and is deemed ready to be locked, the treatment assignments will be uploaded to the main study database, and the database will be locked.

9 STATISTICAL CONSIDERATIONS

9.1 General Considerations

All data collected will be presented in summary tables and/or data listings. Descriptive statistics will be used to present study data. For categorical variables, the number and percentage of subjects in each category will be summarized. Continuous variables will be summarized with the number of observations (n), mean, standard deviation (SD), median, minimum, and maximum values. All data will be presented in listings. Analyses will be performed using SAS v9.4.

9.2 Demographics and Baseline Characteristics

Demographics for the safety analysis set will be presented as summary statistics for age (overall and by subgroups), gender, race/ethnicity, height, and weight by treatment group and all

groups combined. Baseline infectious disease presence or absences and COVID presences or absence will be presented in tabular form. Baseline stool consistency and symptoms will be summarized. All of the above and medical history and physical examination results will be included in data listings.

9.3 Participant Accountability and Protocol Deviations

The disposition of all study subjects will be summarized including the total numbers screened, eligible, randomized, analysis set, withdrawn, and completed. Accountability data including study termination and reason will be provided in a listing for all subjects who were randomized. A listing of all Protocol Deviations will be provided.

9.4 Study Drug Exposure

Study drug is given once per patient. Patient listing will be provided with date and time of administration, whether there was any problem with administration and specification of the problem.

9.5 PK Analysis

PK parameters such as $AUC_{0-\text{defined time}}$, C_{max} , T_{max} , λ_z , and $t_{1/2}$ are presented as summary statistics including mean, standard deviation (SD), geometric mean, median, minimum and maximum. These parameters are defined and will be calculated using WinNonLin 5.2 (Pharsight Corp, Mountain View, CA) using a non-compartmental analysis as follows:

AUC(0-t): Area under the plasma concentration-time curve from time 0 to the time (t) of last quantifiable concentration (C_t) calculated by the log/linear trapezoidal rule.

AUC(0-inf): Area under the plasma concentration-time curve from time 0 extrapolated to infinity. The terminal area from C_t to infinity will be calculated by using the approximation as C_t / λ_z thus $AUC(0-\text{inf}) = AUC(0-t) + C_t / \lambda_z$.

C_{max} : The maximum observed plasma concentration.

T_{max} : The observed time to reach maximum plasma concentration.

λ_z : The terminal-phase exponential rate constant as calculated from the negative slope of the regression line for the terminal linear portion of the LN transformed plasma concentration versus time curve.

$t_{1/2}$: The apparent terminal exponential half-life, calculated as $\ln(2) / \lambda_z$.

Concentration time curves by individual subject and by group geometric means \pm SD will be presented.

9.6 Adverse Events and Serious Adverse Events

AEs will be coded using the most recent version of the Medical Dictionary of Regulatory

Activities (MedDRA) preferred terms and will be grouped by system, organ, and class (SOC) designation. The severity, frequency, and relationship of AEs to study drug will be presented by preferred term by SOC grouping. Listings of each individual AE including start date, stop date, severity, relationship, outcome, and duration will be provided. The duration of the event will be calculated by subtracting the start date of the event from the stop date of the event and adding the integer one. Thus, if an AE started and stopped on the same day, then the duration is 1 day. Or if the AE started one day and stopped the next day, the duration is 2 days.

GI AEs will also be summarized separately including stool consistency scores and presence/absence and severity of other symptoms according to the GI Signs and Symptoms checklist or endoscopy results if applicable. The GI AE scale scoring will be presented as summary statistics by categorical response. The presence, absence, and severity of other signs and symptoms of GI AEs indicative of possible gastric inflammation or erosion including endoscopy results will be presented as numbers and percentages, including if the GI AE triggered a study stopping criteria.

Serious Adverse Events (SAEs): A listing of all participants experiencing SAEs will be provided. This listing will include the subject ID, name of the SAE, treatment group, gender, age, onset day relative to last injection, and outcomes.

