#### **4.9. Benefit/Risk Assessment/Protection Against Risks**

Since this is a Phase 1 study, there are no benefits to the subjects. However, given the current opioid epidemic and the need for safer, more effective non-opioids to treat pain, there are significant benefits to society.

The risks of the study drug are not yet fully known in humans. The nonclinical safety profile of kindolor tosylate has been well characterized through the conduct of genetic toxicology, safety pharmacology, and acute and repeat dose (7-14 days) toxicology studies. Kindolor tosylate is not genotoxic and is not expected to have effects on the central nervous, respiratory, or cardiovascular systems in humans at clinically relevant doses.

The most notable adverse effect associated with kindolor tosylate was the result of local toxicity to the stomach. Repeated oral administration of kindolor tosylate resulted in adverse effects in the stomach in minipigs and to a much lesser extent, in rats. This was characterized initially by soft feces in the minipig. At the end of the dosing period, erosions and ulcerations were observed in the stomachs of rats and minipigs. However, doses that did not cause these effects were identified in both species after repeat dosing over 14-days. Thus, given that single doses, and an enteric coated formulation will be used in this study, the risk of GI toxicity should be low.

Increases in total bilirubin were observed in both rats and minipigs and may be related to the fact that kindolor is a high affinity inhibitor of OATP1B1 and OATP1B3 transporters. There were, however, no correlative histological observations or other clinical chemistry changes, and hepatic effects were reversible upon cessation of dosing. In minipigs only, an increase in renal tubular degeneration/regeneration was noted in both sexes at the two highest doses tested. This renal lesion, commonly observed in nonclinical safety studies, was reversible upon cessation of exposure and was considered non-adverse due to the minimal nature and lack of correlative clinical pathology suggestive of organ dysfunction. Additionally, no alterations in renal parameters (clinical chemistry or histology) were noted in the second minipig study at doses of kindolor tosylate up to 622 mg/kg/day (HED of 444 mg/kg/day).

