#### **11.1.5. Gastrointestinal Adverse Events**

Gastrointestinal (GI) AEs will be assessed as follows:

- Stool Consistency Questionnaire – subject completed questionnaire ([Appendix A](#))
- GI Signs and Symptoms Checklist ([Appendix B](#))
- FOBT
- Open ended questions about AEs that are indicative of gastritis
- Clinical laboratory tests (hematocrit, hemoglobin, blood urea nitrogen (BUN), creatinine, ALT, and AST)
- Endoscopy (if indicated)

A-subject completed Stool Consistency Questionnaire ([Appendix A](#)) that asks 4 questions about GI symptoms will be utilized to assess GI AEs. The responses to the questions are based on a 4-point scale with 0 being no symptom and 3 being a severe symptom. The development of a new symptom or worsening of an existing symptom will be reported as an AE.

In addition, if a subject reports of any of the signs and symptoms of gastritis or potential GI ulcer complications or has a laboratory test result indicative of blood loss as shown in the GI Signs and Symptoms Checklist ([Appendix B](#)), the study gastroenterologist sub-investigator will do a thorough evaluation of the event and perform an endoscopy if it is considered warranted. A signs and symptoms checklist will be reviewed each day starting with Day 1, and then on Days 2, 3, and 7. Presence or absence of each sign or symptom will be recorded and if appropriate, a severity assessment or clinical significance evaluation will be performed.

Clinically significant changes in hematocrit and hemoglobin are defined as decreases of at least 10 percentage points and 2 g/dL, respectively. Clinically significant changes in other clinical laboratory tests will be defined as blood urea nitrogen  $\geq 40$  mg/dL, creatinine  $\geq 1.8$  mg/dL, ALT

and AST  $\geq 3$  times the upper limit of normal. If there is evidence of gastric erosion, ulcer, or bleeding in any subject confirmed by endoscopy or FOBT, the study will be stopped.

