| Physical Examination | X | update | | | X | | | X |
| Height/Weight | X | Weight only | | | | Weight only | | Weight only |
| 12-Lead ECG ^a | X | | X | X | X | X | | X |
| Vital Signs ^b | X | X | X ^c | X | X | X | | X |
| Serum amylase | X | X | | | X | X | | X |
| Serum lipase | X | X | | | X | X | | X |
| Clinical Chemistry ^d | X | X | | | X | X | | X |
| Hematology ^e | X | X | | | X | X | | X |
| Coagulation ^f | X | X | | | X | X | | X |
| Urinalysis ^g | X | X | | | X | X | | X |
| Monitor urine output ^h | | | X | X | X | | | |
| Infectious Diseases ⁱ | X | | | | | | | |
| SARS-CoV-2 Antigen Test ^j | X | | | | | | | |

| | Outpatient | Inpatient | | | | Outpatient | | Early Termination |
|--|------------|---------------|-----------|-----------|------------------|------------|--------------------------------|-------------------|
| Activity | Screening | Clinic Intake | Treatment | Follow-up | Clinic Discharge | Follow-up | Telephone Contact ^a | |
| Study Day | -30 to -2 | -1 | 1 | 2 | 3 | 7±2 | | |
| Pregnancy Test ^k | X | X | | | | X | | X |
| Birth control methods | X | update | | | update | | update | |
| Sperm, ova, donation and breast feeding check | | X | | | | X | X | |
| FOBT | X | X | | | X | X | | |
| Urine Alcohol & Drug Screen ^l | X | X | | | | | | |
| Prior and Concomitant medications ^m | X | X | X | X | X | X | | X |
| Eligibility Checklist | X | Final check | | | | | | |
| Genetics Tests ⁿ | | X | | | | | | |
| Study Drug Administration | | | X | | | | | |
| Blood Samples for PK ^o | | | X | X | X | | | |
| Adverse Events ^p | | | X | X | X | X | | X |
| Stool Consistency | | X | X | X | X | X | | X |
| Final Subject Disposition | | | | | | X | | X |

^a A 12-lead resting ECG will be obtained at Screening, Day 1 prior to dosing, at 2, 6, 12, 24, and 48 hours post dose, and early termination.

^b Vital signs include sitting (3 minutes) blood pressure, and heart rate, and oral temperature, respiration rate, and pulse oximetry.

^c Blood pressure, and heart rate, respiration rate, and pulse oximetry will be taken pre-dose, then at 15, 30, 60 minutes and 2, 4, 6, 12, 24, and 48 hours post dose. Temperature will be taken pre-dose, 24, and 48 hours post dose. All vital signs will be taken at Day 3 before clinic discharge and Day 7.

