9.7 Clinical Laboratory Data

Clinical laboratory test results, urine drug screen results, and pregnancy test results will be reported as summary statistics for each assessment time point. Clinical chemistry, amylase, lipase, hematology, coagulation, urinalysis, FOBT, urine drug screen results, and pregnancy test results will be presented as summary statistics and change from baseline. In addition, change from baseline (shift tables) will also be presented for clinical chemistry, amylase, lipase, hematology, and coagulation data.

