Multiple occurrences of a specific adverse event for a subject are counted once in the frequency for the adverse event. Likewise, multiple occurrences of adverse events within a specific preferred term for a subject are counted once in the frequency for the preferred term.

Programmer's Notes: Order System Organ Class alphabetically and preferred term alphabetically within System Organ Class.

Table 14: Number and Percentage of Subjects with Adverse Events Leading to Withdrawal from the Study

| MedDRA SOC/ Preferred Term | Kindolor 100 mg (N=xx) | Kindolor 300 mg (N=xx) | Kindolor xx mg (N=xx) | Placebo (N=xx) |
|-------------------------------|------------------------------|------------------------------|-----------------------------|-------------------|
| SOC | | | | |
| - Overall - | xx (xx.x%) | xx (xx.x%) | xx (xx.x%) | xx (xx.x%) |
| Preferred term 1 | xx (xx.x%) | xx (xx.x%) | xx (xx.x%) | xx (xx.x%) |
| Preferred term 2 | xx (xx.x%) | xx (xx.x%) | xx (xx.x%) | xx (xx.x%) |

Notes: Percentages are based on the total number of subjects, as given in the column heading.

Multiple occurrences of a specific adverse event for a subject are counted once in the frequency for the adverse event. Likewise, multiple occurrences of adverse events within a specific preferred term for a subject are counted once in the frequency for the preferred term.

Programmer's Notes: Order System Organ Class alphabetically and preferred term alphabetically within System Organ Class.

Table 15: Stool Consistency by Visit

| | | Kindolor 100 mg | Kindolor 300 mg | Kindolor xx mg | Placebo | All subjects |
|---|--|-----------------|-----------------|----------------|--------------|--------------|
| Visit | Characteristic | (N=xx) | (N=xx) | (N=xx) | (N=xx) | (N=xx) |
| Repeat for Treatment, Inpatient Follow-up, Clinic Discharge, Outpatient Follow-up and Early termination | Frequency of Stools per Day | | | | | |
| | Mean (SD) | xx.x (xx.xx) | xx.x (xx.xx) | xx.x (xx.xx) | xx.x (xx.xx) | xx.x (xx.xx) |
| | Median | xx.x | xx.x | xx.x | xx.x | xx.x |
| | Min-Max | (xx-xx) | (xx-xx) | (xx-xx) | (xx-xx) | (xx-xx) |
| | Consistency of Stools per Day | | | | | |
| | Type 1 | xx (xx.x%) | xx (xx.x%) | xx (xx.x%) | xx (xx.x%) | xx (xx.x%) |
| | Type 2 | xx (xx.x%) | xx (xx.x%) | xx (xx.x%) | xx (xx.x%) | xx (xx.x%) |
| | Type 3 | xx (xx.x%) | xx (xx.x%) | xx (xx.x%) | xx (xx.x%) | xx (xx.x%) |
| | Type 4 | xx (xx.x%) | xx (xx.x%) | xx (xx.x%) | xx (xx.x%) | xx (xx.x%) |

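### Bristol stool type and stool frequency are recorded on Day -1 and after dosing, but no planned summary pairs a subject's post-dose answer with his or her own baseline

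*SAP*

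**What the plan says.** The schedule in SAP section 5 places the questionnaire at clinic intake (Day -1), Days 1, 2 and 3, the outpatient follow-up and early termination: "Stool Consistency | | X | X | X | X | X | | X".

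The baseline goes into one table. SAP 9.2 states that "Baseline stool consistency and symptoms will be summarized", and the Baseline Characteristics shell (Table 3) does this. Post-dose answers go into another, "Table 15: Stool Consistency by Visit", whose programming instruction is "Repeat for Treatment, Inpatient Follow-up, Clinic Discharge, Outpatient Follow-up and Early termination". That shell has counts for Bristol Types 1 to 7 and for each symptom category, and mean, SD, median and range for stool frequency. It has no Day -1 row, change row or shift row. The governing text in SAP 9.6 is "The GI AE scale scoring will be presented as summary statistics by categorical response".

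Other endpoints are treated differently. Under SAP 9.7, laboratory tests and FOBT get change from baseline, and "change from baseline (shift tables) will also be presented for clinical chemistry, amylase, lipase, hematology, and coagulation data". SAP 9.8 plans change from baseline for vital signs and ECG.

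Protocol 11.1.5 gives one within-subject rule for the questionnaire: "The development of a new symptom or worsening of an existing symptom will be reported as an AE". It is attached to four questions scored 0 to 3.

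**The concern.** Protocol 4.9 names local stomach toxicity as the most notable adverse effect in animals and says of it: "This was characterized initially by soft feces in the minipig". Softening is therefore the stool change most closely tied to the toxicity the trial is watching for, and Bristol type is the item that measures it.

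Whether stools softened or became more frequent after dosing is a question about each subject against his or her own baseline. If the report shows only separate distributions at each visit, the number of subjects who changed must be worked out later from a listing. What counts as a change, which visit is used and what the denominator is would then be chosen after the data are seen.

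**Working it through.** **1. The plan's own figure.** Protocol 12.4 and SAP 7 give the chance of at least one event among 6 active subjects as 47%, 62%, 74% and 82% at true rates of 10%, 15%, 20% and 25%. With P = 1 − (1 − p)^6 the results are 46.9%, 62.3%, 73.8% and 82.2%, which match. This rationale counts subjects with an event. For a Bristol shift, no planned table supplies that count.

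**2. The endpoint list, item by item** (protocol 9.1, SAP 3.3).
- AEs: collected after dosing, so no baseline applies.
- GI Signs and Symptoms Checklist: reviewed from Day 1 after dosing (Appendix B), so no pre-dose administration is scheduled. The Listing 12 shell nevertheless shows Screening and Day -1 rows.
- Laboratory data and FOBT: change from baseline in SAP 9.7, although the FOBT rows of Table 20 show only by-visit counts.
- ECG and vital signs: change from baseline in SAP 9.8.
- Urine output: the first collection starts on Day 1, so there is no pre-dose period.
- Stool questionnaire: Day -1 assessment scheduled, no change summary in the text.

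**3. What the AE rule covers.** In Appendix A the items scored 0 to 3 are urgency, abdominal pain or discomfort, bloating, and interference with activities. Stool frequency and Bristol type are separate items without that scale, and no worsening rule expressly covers them.

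**4. What by-visit counts can identify.** Let b be a subject's Day -1 Bristol type and a the type at one post-dose visit. The number softened is S = number of subjects with a > b. Tables 3 and 15 fix the set of b values and the set of a values but not the pairing, so S can take any value that some pairing allows. The counts below are illustrative assumptions with n = 6.

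| Day -1 | Post-dose | Subjects softened |
|---|---|---|
| 3 Type 3, 3 Type 4 | same | 0 to 3 (0% to 50%) |
| 2 each of Types 3, 4, 5 | same | 0 to 4 (0% to 66.7%) |
| 2 each of Types 3, 4, 5 | 1 Type 3, 2 Type 4, 2 Type 5, 1 Type 6 | 1 to 5 (16.7% to 83.3%) |
| 6 Type 4 | 3 Type 4, 3 Type 6 | exactly 3 (50%) |

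In the first row, S = 0 if nobody changed. S = 3 if all three Type 3 subjects moved to Type 4 and all three Type 4 subjects moved to Type 3.

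Across all 28 × 28 = 784 pairs of count distributions on Types 3 to 5, given equal weight, the counts fix S in 234 (30%). In a random sample of 1,500 pairs on Types 2 to 6, they fix it in 207 (14%). These shares describe the tables and are not predictions for this trial.

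**5. Across visits.** One Type 6 stool in six subjects at each of four post-dose visits could be one subject (1/6 = 16.7%) or four different subjects (4/6 = 66.7%).

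**6. Stool frequency.** If the same subjects answer at both visits, the difference of the visit means equals the mean change. The spread of the changes and the number of subjects with an increase cannot be recovered from the tables.

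**The case against.** Most of the case on the other side stands as a limit on the point.

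- A reader might infer that this is the only safety assessment with a baseline and no change analysis. The documents do not support that. Physical examination is a safety criterion in the protocol synopsis and appears under SAP 5.2. It is done before and after dosing (protocol 11.13) and gets only a screening listing. The statement holds for the formal endpoint list only.
- A reader might infer that the planned output cannot show who changed. Listing 13 gives frequency, consistency and symptom severity by subject and visit, with a Day -1 row, and groups of six can be read by eye. Some count patterns also settle the answer, as the last row of the table shows. What is missing is a prespecified summary, not the information.
- A reader might infer that questionnaire worsening goes uncounted altogether. The 0-3 items reach the AE tables, which count each subject once. The endpoint itself is worded in terms of answers that point to a GI AE, and the general AE definition could also pick up a marked stool change. Even so, nothing states when a Bristol or frequency change qualifies.
- A reader might infer that usable paired data are certainly being collected. The Bristol item in Appendix A asks for the type matching the subject's least firm usual stool before entering the study, and no post-dose wording is shown. Read literally, every visit asks about the same pre-study period, and a shift table would not measure post-dose softening.
- The soft feces followed repeated dosing in minipigs, whereas this trial gives single enteric-coated doses. FOBT, the checklist, laboratory tests and endoscopy where indicated also monitor the stomach. This lowers the stakes but does not make unpaired counts the better summary.

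**Conclusion.** The point holds in a limited form. The SAP plans no summary linking Bristol type or stool frequency to a subject's own Day -1 answer, and by-visit summaries in groups of six generally leave the number of subjects who changed undetermined, by up to three or more of six in ordinary-looking patterns. The 0-3 items are already covered through AE reporting, and Listing 13 allows pairing by hand.

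The size rests on illustrative counts, since the documents give no expected Bristol distribution. The value of the repair rests on post-dose forms asking about the post-dose period. No stated figure in the plan changes. This is an inexpensive improvement that should be made, not a defect that undermines the trial.

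**What to change.** First, confirm how the Bristol item reads on post-dose forms. Reword it if it carries the printed text, so that it refers to the period since dosing or since the last assessment. If subjects have already completed the printed form, state in the SAP how they were instructed and whether the answers can be read as post-dose.

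Then add to SAP 9.6 and to the Table 15 shell, for each dose (n = 6) and pooled placebo (2 × 4 = 8):
- a shift table from Day -1 Bristol type to the loosest (highest-numbered) post-dose type, over all post-dose visits including early termination;
- change from Day -1 in stool frequency;
- the number and percentage of subjects with any upward shift in Bristol type, and likewise in frequency.

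Keep the by-visit table. Shift tables for the 0-3 items are optional. These are summary definitions and do not alter what is reported as an AE.

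State the drawback in the SAP: one baseline answer set against the worst of several post-dose answers shows some upward shift by chance. If a subject's one baseline and four scheduled post-dose answers were exchangeable, the baseline would be at least tied for highest with probability of at least 1/5, so the chance of an apparent upward shift could reach 4/5 at most. Ties between answers bring it down. The counts should therefore be read against pooled placebo.

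The cost is SAP wording, one extra table and a check or revision of one form item. No extra visits or subjects are needed.
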